### 3.6 Biomarker variables

PD-L1 expression status used as stratification factor for randomization will be assessed for evaluable patients according to following criteria:

- Positive:  $\geq 25\%$  tumor cell membrane positivity for PD-L1 at any intensity above background staining as noted on the corresponding negative control.
- Negative:  $< 25\%$  tumor cell membrane positivity for PD-L1 at any intensity above background staining as noted on the corresponding negative control.

## 4. ANALYSIS METHODS

The main hypothesis to be tested is improved OS in PD-L1 TC/IC high subgroup population treated with MEDI4736 monotherapy and SoC.

The study will be considered positive (a success) if this hypothesis is statistically significant. A multiple testing procedure has been implemented to strongly control the type I error rate at 5%

Additional hypotheses will be tested using a multiple testing procedure, which is outlined in [Figure 4](#). The procedure will define the significance levels that should be applied to the interpretation of the nominal p-values.

The formal statistical analysis will be performed to test the main hypotheses:

- $H_0$ : No difference between MEDI4736 monotherapy and SoC
- $H_1$ : Difference between MEDI4736 monotherapy and SoC

The primary objective is OS in the PD-L1 TC/IC high subgroup for MEDI4736 monotherapy versus SoC. The study was originally sized to characterize the OS benefit of MEDI4736 + tremelimumab combination therapy versus SoC.

With CSP version 12, the primary objective was changed to characterize the OS benefit of MEDI4736 monotherapy versus SoC in the PD-L1 TC/IC high subgroup, due to this change the analysis of OS will be performed when approximately 147 death events from the PD-L1 TC/IC high subgroup population have occurred in approximately 172 patients (85% maturity) across the MEDI4736 monotherapy therapy and SoC treatment groups. All other endpoints will be analysed at this time. No interim analyses will be performed for any efficacy endpoint

### Multiple testing strategy

In order to strongly control the type I error at 5% 2-sided, a multiple testing procedure (MTP) will be used across the primary endpoint (OS), treatment regimens (MEDI4736 monotherapy, MEDI4736 + tremelimumab, and SoC), and across the analysis populations (PD-L1 TC/IC

[figure not shown]
high subgroup, low risk of EM subgroup, ctDNA TMB high ( $\geq 16$  mut/Mb) subgroup and all-comers). If the highest-level hypothesis in the MTP is statistically significant, the next hypothesis in the hierarchy will then be tested as shown in [Figure 4](#)).

Hypotheses will be tested using a hierarchical multiple testing procedure to control for the overall type I error at the 0.05 level (two-sided). With this approach, hypotheses will be tested in a predefined order (sequentially rejective manner at  $\alpha=0.05$ ) as outline in [Figure 4](#).

Hypotheses in the hierarchy will be to test MEDI4736 monotherapy versus SoC in the PD-L1 TC/IC high subgroup population followed by MEDI4736 monotherapy versus SoC in the low risk of EM subgroup population, then MEDI4736 monotherapy versus SoC in the ctDNA TMB high ( $\geq 16$  mut/Mb) subgroup, then MEDI4736 + tremelimumab combination therapy versus SoC in the ctDNA TMB high ( $\geq 16$  mut/Mb) subgroup, then MEDI4736 monotherapy versus SoC in all-comers and finally MEDI4736 + tremelimumab combination therapy versus SoC in all-comers. All tests will be at the two-sided 5% alpha level and the procedure will stop at the first failure to find statistically significant evidence of superiority or if tests of all hypotheses show statistically significant evidence of superiority over SoC.

Note: the comparisons of MEDI4736 + tremelimumab combination therapy versus MEDI4736 monotherapy and the comparison of MEDI4736 + tremelimumab combination therapy versus SoC (in the PD-L1 TC/IC high subgroup and low risk of EM subgroup) will not be included in the MTP, and therefore will not be conducted under strict alpha control.

**Figure 4 Multiple testing procedure for controlling the type 1 error rate**

Combo MEDI4736 + tremelimumab combination therapy; EM Early mortality; IC tumor associated immune cell; Mono MEDI4736 monotherapy; OS Overall survival; PD-L1 Programmed death ligand 1; SoC Standard of Care; TC tumor cell; TMB Tumor Mutational Burden.

#### 4.1 General principles

IVRS based stratification factors will be used for the analysis of primary objectives as well as the analyses for other secondary objectives namely; PFS, ORR, PFS2, TFST, TSST, Time to

deterioration of EORTC QLQ-C30 and EORTC QLQ-H&N35, improvement rate of EORTC QLQ-C30 and EORTC QLQ-H&N35.

The subgroup analyses for the stratification factors as well as all other factors will be based on values recorded on the CRF. If there is >10% discordance in stratification factors as recorded in IVRS versus the Case Report Form (CRF), then a sensitivity analysis of the primary objectives, will be performed using CRF based stratification factors. For this sensitivity analysis if there are missing baseline covariate values, patients will be retained in the analysis by including the missing data as another stratification level.

Other general principles that will be followed throughout the study include the following:

- Descriptive statistics will be used for all variables, as appropriate, and will be presented by treatment group. Continuous variables will be summarized by the number of observations, mean, standard deviation, median, minimum, and maximum. Categorical variables will be summarized by frequency counts and percentages for each category.
- Unless otherwise stated, percentages will be calculated out of the population total for the corresponding treatment arm.
- For continuous data the mean and median will be rounded to 1 additional decimal place compared to the original data. The standard deviation will be rounded to 2 additional decimal places compared to the original data. Minimum and maximum will be displayed with the same accuracy as the original data.
- For categorical data, percentages will be rounded to 1 decimal place.
- Results of all statistical analysis will be presented using a 95% confidence interval (CI) and 2-sided p-value, unless otherwise stated.
- All models will include 3 treatment groups and any pairwise comparisons will then be extracted.
- SAS® version 9.4 or higher will be used for all analyses.
- Palliative radiation will not be considered as a subsequent therapy.

Baseline will be the last assessment of the variable under consideration prior to the intake of the first dose of IP, except for efficacy variables. For efficacy variables, baseline is defined as the last visit prior to randomization. For PRO variables, baseline will be defined as the latest evaluable assessment on or prior to date of first dose.

Outcomes variables will be summarized and analyzed based on the analysis populations detailed in Tables 6 and 12. All outputs will be summarized by treatment arm.

In terms of retreatment, individual efficacy response data from the re-treatment phase will only be listed, however data from retreatment will be included in all PRO analyses. Any

derivations relative to baseline (e.g., day, RECIST derivations) in the retreatment period will be relative to the baseline scan prior to the retreatment period.

Note that the AEs, SAEs and AESI/AEPI events will be reported regardless of whether the event occurred during re-treatment period or not. Additionally, if there are sufficient numbers of retreated patients to warrant separate summaries following combinations of summaries would also be produced:

The period for assessing safety data from the retreatment phase will start at the date of first dose in the retreatment phase

- A small set of headline summaries of AE data from the retreatment phase only.

Table 12 details which efficacy endpoints are to be analyzed, together with pre-planned sensitivity analyses indicating which analysis is regarded as primary for that endpoint. Formal statistical analysis will be done for only OS endpoint. Nominal p-values will be provided for all other endpoint and sensitivity analyses. No adjustments for multiple testing of endpoints or subgroups will be made.

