### 1.3 Number of subjects

The sample size for this study was selected to be consistent with the research hypothesis as described in Section 8.5 of the Clinical Study Protocol (CSP).

The study will enroll approximately 1016 patients in order to randomize 760 eligible patients in a 2:1:1 ratio (380:190:190 patients) to MEDI4736 + tremelimumab combination therapy, MEDI4736 monotherapy, or SoC respectively.

The study was originally sized to characterize the OS benefit of MEDI4736 + tremelimumab combination therapy versus SoC in all-comers (i.e., regardless of PD-L1 tumor expression status) and in PD-L1 TC/IC subgroup population. The sizing assumes a 3-month delay in separation of the OS curves between each arm, hence the use of average HRs.

With amendment 11 (CSP version 12) the primary objective was changed to characterize the OS benefit of MEDI4736 monotherapy versus SoC in the PD-L1 TC/IC high subgroup. Due to this change the primary analysis of OS will be performed when approximately 147 death events have occurred in approximately 172 patients (85% maturity) across the MEDI4736 monotherapy and SoC treatment groups in the PD-L1 TC/IC high subgroup population. The number of patients (172) assumes that 45% of patients randomized are within this subgroup. No interim efficacy analyses will be performed in this study.

If superiority over SoC is found, a hierarchical multiple testing procedure (MTP) will be employed to strongly control for the overall type I error at the 5% alpha level (two-sided), as shown in Section 4, Figure 4.

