#### **4.2.4 Objective response rate**

The ORR will be based on the programmatically derived RECIST 1.1 using site investigator tumor data. The ORR will be compared between MEDI4736 monotherapy versus SoC using logistic regression models adjusting for the same factors as the primary endpoint (PD-L1 status, tumor location, and smoking history). The results of the analysis will be presented in terms of an odds ratio together with its associated profile likelihood 95% CI (e.g. using the option 'LRCI' in SAS procedure GENMOD) and p-value (based on twice the change in log-likelihood resulting from the addition of a treatment factor to the model).

A similar analysis will be performed for the comparison between MEDI4736 + tremelimumab combination versus SoC and between MEDI4736 + tremelimumab combination versus MEDI4736 monotherapy in for the analysis populations detailed in Table 12.

Summaries will be produced that present the number and percentage of patients with a tumor response (CR/PR). Overall visit response data will be listed and summarized over time for all patients (i.e., the FAS).

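### Read literally, the SAP's three-arm model rule and its ORR likelihood-ratio rule give a 2-df p-value that does not test the pairwise comparison it is printed beside

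*SAP*

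**What the plan says.** SAP 4.1 (General principles) sets a rule for every model: "All models will include 3 treatment groups and any pairwise comparisons will then be extracted". The same section asks for a 95% interval and a two-sided p-value by default, and says of everything outside the formal OS testing: "Nominal p-values will be provided for all other endpoint and sensitivity analyses".

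SAP 4.2.4 (Objective response rate) names the comparison: "The ORR will be compared between MEDI4736 monotherapy versus SoC using logistic regression models adjusting for the same factors as the primary endpoint". It reports an odds ratio with a profile-likelihood 95% interval (the LRCI option of SAS GENMOD is given as an example) and a p-value "based on twice the change in log-likelihood resulting from the addition of a treatment factor to the model". For the other pairs it adds: "A similar analysis will be performed for the comparison between MEDI4736 + tremelimumab combination versus SoC", and likewise for combination versus monotherapy.

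Protocol 8.5.2.2 has the same likelihood-ratio wording and lists the three comparisons one by one, but the Protocol has no three-arm model rule. SAP 4.2.12.1 and 4.2.12.2 analyse the QLQ-C30 and QLQ-H&N35 improvement rates with the logistic model described for ORR.

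None of these sections gives the degrees of freedom of the test or describes a contrast step for the p-value.

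**The concern.** The interval and the p-value in SAP 4.2.4 are defined on different objects. A profile-likelihood interval belongs to one coefficient, hence to one pair of arms. The change in log-likelihood from adding the treatment factor belongs to the whole factor. With two arms these coincide. With the three arms that SAP 4.1 requires, they do not.

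A programmer who follows both rules to the letter would print a pairwise odds ratio and interval beside an omnibus p-value. That p-value could be small while monotherapy and SoC respond identically, because the combination arm differs from both. It could also be large when monotherapy and SoC truly differ, because the second degree of freedom dilutes the test. Either way the p-value could contradict the interval next to it. ORR is a secondary objective in four populations, and the PRO improvement rates inherit the method.

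**Working it through.** **No plan figure to reproduce.** The documents give no ORR sample size, power or degrees of freedom. The check is structural, followed by an illustration of size.

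**Inputs**
- Allocation (SAP 1.3): "randomize 760 eligible patients in a 2:1:1 ratio (380:190:190 patients" to combination, monotherapy and SoC.
- PD-L1 TC/IC high share (SAP 1.3): 45%. 0.45 × 380 = 171 and 0.45 × 190 = 85.5, taken as 86 as in SAP Table 5.
- SoC response rate: 36%, reported for EXTREME in Protocol 1.1.1.
- A lower monotherapy rate for the power check: 18%, reported for MEDI4736 in PD-L1-positive SCCHN in Protocol 1.2.5.
- Combination response rate: an assumption. The documents give no SCCHN figure, so a range is shown.

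**Step 1: which hypothesis each test addresses.** Let SoC be the reference, with treatment coefficients b_M (monotherapy) and b_C (combination).
- Adding the treatment factor: LR = 2 × [logL(full) − logL(no treatment term)]. The null is b_M = b_C = 0, with 2 df. The expression does not depend on which pair is being reported, so all three comparisons receive the same value.
- Named contrast, monotherapy versus SoC: LR = 2 × [logL(full) − logL(monotherapy and SoC constrained equal, combination free)]. The null is b_M = 0, with 1 df.

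**Step 2: one data set by hand.** SoC 31/86, monotherapy 31/86, combination 31/171, no covariates. For each arm, logL = x ln(x/n) + (n − x) ln(1 − x/n).
- Full model: −56.217 − 56.217 − 80.941 = −193.375.
- No treatment term (93/343): −200.445. LR = 2 × 7.070 = 14.14 on 2 df, p = 0.0009.
- Monotherapy and SoC merged (62/172), combination free: −193.375. LR = 0 on 1 df, p = 1, odds ratio 1.00.

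Adding three invented binary covariates to the same counts gives a monotherapy/SoC odds ratio of 0.98; 2-df LR 14.35, p = 0.0008; 1-df contrast LR 0.003, p = 0.96; separate two-arm model p = 0.93.

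**Step 3: how often this happens.** Simulated trials without covariates (400,000 per scenario), monotherapy = SoC = 36%, arms 171:86:86. Proportion with p < 0.05:

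| Assumed combination ORR | 2-df test | 1-df contrast |
|---|---|---|
| 42% | 16% | 5% |
| 36% | 5% | 5% |
| 31% | 13% | 5% |
| 28% | 28% | 5% |
| 26% | 42% | 5% |
| 25% | 50% | 5% |
| 18% | 94% | 5% |

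In all-comers (380:190:190) the 2-df test rejects in 5% of trials at 36%, 77% at 26% and nearly 100% at 18%; the 1-df contrast again stays at 5%.

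**Step 4: when monotherapy truly differs.** SoC 36%, monotherapy 18%, arms 171:86:86. The 1-df contrast has 77% power whatever the combination does. The 2-df test has 85%, 67% and 85% at combination rates of 18%, 27% and 36%.

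**The case against.** The strongest reply is that a sensible programmer would not produce the omnibus p-value. The SAP 4.1 sentence goes on to call for pairwise extraction. SAP 4.2.4 attaches the odds ratio, interval and p-value to one named comparison and treats the other two as analyses in their own right, which fits poorly with a single shared p-value. The Protocol's version, without the three-arm rule, reads naturally as a two-arm, 1-df test. All of this stands as evidence of intent. A reader might infer that the plan prescribes an omnibus test; it does not, since 2 df is nowhere stated and a 1-df contrast is compatible with the text. Nor is a pairwise likelihood-ratio p-value unobtainable from a three-arm model: Step 2 computes one. What the reply leaves open is that the only explicit p-value rule, followed as written in the required model, tests a different hypothesis.

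The second reply concerns size. The large percentages need a combination arm that responds well below both other arms, whereas Protocol 1.2.5 expects adding tremelimumab to raise response. That is fair: 94% is an extreme of an assumed range. With all arms equal the 2-df test holds its 5% level, and a modest combination advantage (42%) gives 16%.

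Third, the consequences are bounded. ORR p-values are nominal, study success rests on OS, and the five Bonferroni-tested PRO endpoints in SAP 4.2.12 are times to deterioration, not improvement rates. This stands in full.

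A reader might also infer that the three-arm rule undermines OS and PFS. The documents do not support that. SAP 4.2.1 and 4.2.3 take p-values from a stratified log-rank test and hazard ratios from a stratified Cox model, not from the ORR likelihood-ratio rule, and a pairwise contrast extracted from a three-arm model is an accepted analysis.

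**Conclusion.** The point holds as a conflict between two stated rules. Applied literally together, SAP 4.1 and 4.2.4 yield a 2-df test of any difference among three arms, printed beside a pairwise odds ratio and interval. A 1-df contrast was probably intended, but the p-value rule does not say so.

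The structural result needs no assumption beyond the literal reading. The size does: it rests on monotherapy and SoC both at 36%, an assumed combination rate, the 45% subgroup share and no covariates. On that basis, false significance for monotherapy versus SoC in the PD-L1-high subgroup runs from 5% to 94% as the combination rate moves between 42% and 18%, with the minimum where all arms are equal. Where a true difference exists, power can fall from 77% to 67%. The reach is limited to nominal ORR p-values and the PRO improvement-rate p-values. It should be corrected because even a nominal p-value must test the comparison it accompanies, and a prespecified plan should not leave that choice to programming.

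**What to change.** In SAP 4.2.4, state that the p-value for each ORR comparison is the 1-df likelihood-ratio test of that named pairwise contrast: the full three-arm model against the model in which those two arms are constrained to be equal and the third is left free. In SAP 4.2.12.1 and 4.2.12.2, state that the improvement-rate p-values follow the same definition.

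Keep the three-arm rule in SAP 4.1 and leave the OS and PFS analyses as they are; nothing here calls for refitting them on two arms. The cost is one or two sentences of SAP wording, with no extra data and no effect on patients.

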**Table 12 Pre-planned statistical and sensitivity analyses to be conducted**

Endpoints Analyzed	Notes
OS	Stratified log-rank tests and Cox proportional method for: Primary objective 
 
- MEDI4736 monotherapy versus SoC in the PD-L1 TC/IC high subgroup (stratified by PD-L1 status, tumor location, and smoking history)
 
 Secondary objectives 
 
- MEDI4736 monotherapy versus SoC in the low risk of EM subgroup, ctDNA TMB high (<math>\geq 16</math> mut/Mb) subgroup and all-comers; (stratified by PD-L1 status, tumor location, and smoking history)
 
- MEDI4736 + tremelimumab combination therapy versus SoC in the PD-L1 TC/IC high subgroup, low risk of EM subgroup, ctDNA TMB high (<math>\geq 16</math> mut/Mb) subgroup and all-comers (stratified by PD-L1 status, tumor location, and smoking history)
 
- MEDI4736 + tremelimumab combination therapy versus MEDI4736 monotherapy in the PD-L1 TC/IC high subgroup, low risk of EM subgroup, ctDNA TMB high (<math>\geq 16</math> mut/Mb) subgroup and all-comers; (stratified by PD-L1 status, tumor location and smoking history)
 
 Sensitivity analysis: 
 
- Sensitivity analysis using the stratified Max-combo test
 

Endpoints Analyzed	Notes
PFS	
Stratified log-rank tests and Cox proportional method for:            Secondary objectives using investigator assessments (RECIST 1.1):
 
 
- MEDI4736 monotherapy versus SoC for the PD-L1 TC/IC high subgroup; low risk of EM subgroup, ctDNA TMB high (<math>\geq 16</math> mut/Mb) subgroup and all-comers; (stratified by PD-L1 status, tumor location and smoking history)
 
- MEDI4736 + tremelimumab combination therapy versus SoC for PD-L1 TC/IC high subgroup; low risk of EM subgroup, ctDNA TMB high (<math>\geq 16</math> mut/Mb) subgroup and all-comers; (stratified by PD-L1 status, tumor location, and smoking history)
 
- MEDI4736 + tremelimumab combination therapy versus MEDI4736 monotherapy for the PD-L1 TC/IC high subgroup; low risk of EM subgroup, ctDNA TMB high (<math>\geq 16</math> mut/Mb) subgroup and all-comers; (stratified by PD-L1 status, tumor location and smoking history)
 
 
Sensitivity Analyses:
 
 
- Sensitivity analysis based on RECIST 1.1 modified for confirmation of progression using site investigator assessments
 
- Sensitivity analyses using BICR assessments (RECIST 1.1)
 

OS12, OS18 and OS24	
Secondary analysis:            Kaplan-Meier estimates at 12, 18 and 24 months for:
 
 
- MEDI4736 monotherapy therapy versus SoC for the PD-L1 TC/IC high subgroup; low risk of EM subgroup, ctDNA TMB high (<math>\geq 16</math> mut/Mb) subgroup and all-comers
 
- MEDI4736 + tremelimumab combination therapy versus SoC for the PD-L1 TC/IC high subgroup; low risk of EM subgroup, ctDNA TMB high (<math>\geq 16</math> mut/Mb) subgroup and all-comers
 

ORR	
Logistic regression for:            Secondary objectives
 
 
- MEDI4736 monotherapy therapy versus SoC for the PD-L1 TC/IC high subgroup; low risk of EM subgroup, ctDNA TMB high (<math>\geq 16</math> mut/Mb) subgroup and all-comers using site investigator RECIST 1.1 assessments
 
- MEDI4736 + tremelimumab combination therapy versus SoC for the PD-L1 TC/IC high subgroup; low risk of EM subgroup, ctDNA TMB high (<math>\geq 16</math> mut/Mb) subgroup and all-comers using site investigator RECIST 1.1 assessments
 
- MEDI4736 + tremelimumab combination therapy versus MEDI4736 monotherapy for the PD-L1 TC/IC high subgroup; low risk of EM subgroup, ctDNA TMB high (<math>\geq 16</math> mut/Mb) subgroup and all-comers using site investigator RECIST 1.1 assessments
 

BoR	
Secondary objective            Descriptive statistic: N (%) using site Investigator data (RECIST 1.1) for all-comers and the PD-L1 TC/IC high subgroup populations

DoR	
Secondary objective            Descriptive statistics and Kaplan-Meier plot for all-comers and the PD-L1 TC/IC high subgroup populations

Endpoints Analyzed	Notes
TTR	Secondary objective: Kaplan-Meier plots and estimates using site investigator data (RECIST 1.1) for all-comers and the PD-L1 TC/IC high subgroup populations
APF6 and APF12	Secondary objective: Kaplan-Meier estimate of PFS at 6 and 12 months for all-comers and the PD-L1 TC/IC high subgroup populations
PFS2	Secondary objective: Stratified log-rank test for all-comers and the PD-L1 TC/IC high subgroup populations
TFST and TSST	Secondary objective: Stratified log-rank test for all-comers and the PD-L1 TC/IC high subgroup populations
Time to deterioration EORTC QLQ-C30 and EORTC QLQ-H&N35 endpoints)	Stratified log-rank test for all-comers and the PD-L1 TC/IC high subgroup populations
Improvement rate (EORTC QLQ-C30 and EORTC QLQ-H&N35 endpoints)	Logistic regression For all-comers and the PD-L1 TC/IC high subgroup populations
Average change from baseline (EORTC QLQ-C30 and EORTC QLQ-H&N35 endpoints)	Mixed effect model repeated measurement (MMRM) analysis. Descriptive statistics including change from baseline for all-comers and the PD-L1 TC/IC high subgroup populations

APF12 Proportion of patients alive and progression free at 12 months; BICR Blinded Independent Central Review; DoR Duration of response; EM Early mortality; EORTC European Organisation for Research and Treatment of Cancer; EQ-5D-5L EuroQol 5-Dimension, 5-Level health state utility index; HR Hazard ratio; ITT Intent-to-Treat; ORR Objective response rate; OS Overall survival; OS12 Proportion of patients alive at 12 months after randomization; OS18 Proportion of patients alive at 18 months after randomization; OS24 Proportion of patients alive at 24 months after randomization; ctDNA circulating tumor DNA; PD-L1 Programmed death ligand 1; PFS Progression-free survival; QLQ-C30 30-item core quality of life questionnaire; QLQ-H&N35 35-item head and neck quality of life questionnaire; RECIST 1.1 Response Evaluation Criteria in Solid Tumors version 1.1; TTR Time to response, MMRM Mixed effect model repeat measurement TMB Tumor Mutation Burden;

